to provide prompts when a student is unsure how to perform a certain step. After completion of the assessment, the VR group will be asked to fill out an objective questionnaire (Appendix 2) based on the standardised USE questionnaire [2] to assess baseline characteristics such as prior experience/training and the usefulness, satisfaction, and ease of use of the VR training modality. Participants from the control group will be given the option to also perform the VR training, and subsequently fill a USE questionnaire about their experience with VR.

Expert Arm

Expert participants will not be randomised, and will all perform the VR-ECMO sim before completing the USE questionnaire. Their data will be used for the face and content validity portion of this study.

Randomisation

Participants in the novice arm will be randomly assigned to either interventional or control group, using <https://www.randomizer.org/> as stated above to generate a group allocation for the participant according to their study ID number.

Blinding

Participants will not be blinded as the differences in the differing nature of the intervention versus control group do not allow for this. Selected study personnel, including those physically facilitating both groups during the intervention phase will not be blinded, as again the study design does not allow for this. Study personnel who facilitate the physical assessment for the novice arm, perform data collection & analysis, including the expert assessor for the video recording, will be blinded.

Burden and risks

We do not foresee any risks or burdens incurred with participation, aside from mild nausea which may occasionally occur during a virtual reality experience. This typically subsides quickly once the head mounted display is removed.

Recruitment and consent

Our study will recruit from two populations for the expert and novice arms of this study. For the former, 10 experts who are experienced perfusionists/intensivists with more than 6 years of experience with ECMO will be included. For the novice arm, the population will include intensive care nurses & cardiothoracic surgery nurses who work at one of the academic hospitals in the Netherlands, with no prior experience with ECMO. We calculated a required sample size of 44 novice participants (22 per group) in order to likely achieve statistically significant results.

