5.1. Research methods

Data will be extracted using online questionnaires. These questionnaires will be built in Microsoft Forms, the results from which are sorted in Microsoft Sharepoint. In this way, results are automatically added when a form is completed, and assigned to the correct row using the participant's study ID, assigned to them once they are recruited. Video footage of the physical assessments will be filmed with a camera, before the footage is locally stored on the V drive, and also a backup of the footage is made in Sharepoint.

Once the study is complete, an archive of the study data will be created, and stored for 10 years using the facilities afforded to us by the Erasmus MC.

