8.3 Exception consent

N/A

9. Handling and storage of data / images / sound recordings / photos / film recordings

Data / images / sound recordings / photos / film recordings

Please describe which data / images / sound recordings / photos / film recordings is/are used, are they obtained for regular healthcare purposes or in the context a research project, or a combination.

In line with Erasmus MC guidelines, all video footage recordings will be kept 10 years after it is collected. The videos of the assessments will be stored on Microsoft Sharepoint, with filenames labelled only with the participants' study ID. Only the PI, research coordinator, and the expert who will assess the videos will be granted access to them.

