9.1 Privacy protection

Describe how subject's privacy is protected. Describe how, when and by whom data is coded (unique code without initials or date of birth) and how the key table is safeguarded, mention the General Data Protection Regulation.

The handling of data will comply with the EU General Data Protection Regulation and the Dutch Act on Implementation of the General Data Protection Regulation (in Dutch: Algemene Verordening Gegevensbescherming en Uitvoeringswet Algemene Verordening Gegevensbescherming. A key table is produced and stored on Microsoft Sharepoint with only the PI and Research Coordinator who will be granted access to it. The rest of the data is stored in a separate table containing no identifiable personal information. The latter database includes all of the data from the questionnaires and the results from the assessments. The final data include the videos of the assessment, which stored on sharepoint, labelled only with the participants study ID. Only the PI, research coordinator, and the expert who will assess the videos will be granted access to them.

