Appendix 2 - User Experience USE Questionnaire

		1. Fully disagree	2. Disagree	3. Neutral	4. Agree	5. Fully agree	N/A
	Usefulness						
1	I learned a lot from this simulation about how to perform an ECMO circuit check						
2	The training helped me being more confident in managing ECMO patients						
3	The training helped me remember the steps an ECMO circuit check						
4	After the training, I have enough knowledge to take the lead in an ECMO circuit check						
	Satisfaction						
6	I enjoyed participating in this ECMO simulation						
7	I was satisfied with the quality of this simulation						
8	I would recommend using this simulation to other colleagues						
9	I would prefer VR training additionally to conventional training (shadowing an expert)						
10	I would prefer VR training instead of conventional training (shadowing an expert)						
	Ease of use						

11	The software is easy to use						
12	I learned to use it quickly						
13	The interaction with the software felt intuitive						
14	I can use the software without written instructions						
Immersiveness							
15	I was not distracted during the training						
16	The simulator was realistic						
17	I felt like I was in a real ICU box						
18	I was interested in the progress of the events within the simulation						
19	I felt actively involved in the patient scenario of the training						

Please list and rank, in order of importance from most (1) to least (3), the advantages and disadvantages of training to use an ECMO machine in VR:

Advantages:

- 1.
- 2.
- 3.

Disadvantages:

- 1.

2.

3.

Do you have any additional suggestions or recommendations for enhancing or adding new features to the simulation?

Thank you for participating

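### Blinding of data handling and analysis is not protected as described, and blinding of the video scoring is not assured

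*Combined protocol and SAP*

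**What the plan says.** **Who is blinded.** The Summary (Blinding) accepts that participants and the staff who deliver the training know the arm. It then says that staff who run the novice test or "perform data collection & analysis, including the expert assessor for the video recording, will be blinded".

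**Who completes the USE form.** Under Novice Arm in the Summary: "After completion of the assessment, the VR group will be asked to fill out an objective questionnaire (Appendix 2"). For the other arm: "Participants from the control group will be given the option to also perform the VR training", with the form to follow if they do. Appendix 2 asks about the simulation throughout, and two items begin "I would prefer VR training", so a completed form shows that the person has used VR.

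**Where the form goes.** Section 5.1 says that questionnaire "results are automatically added when a form is completed, and assigned to the correct row" by means of the study ID. Section 9.1 describes a key table and a second, coded table, and says of the second: "The latter database includes all of the data from the questionnaires and the results from the assessments".

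**How allocation and videos are indexed.** The Summary (Randomisation) uses an online tool to "generate a group allocation for the participant according to their study ID number". Section 9 stores the assessment videos "with filenames labelled only with the" study ID. Sections 9 and 9.1 give video access to the PI, the research coordinator and the expert who scores the videos. Section 9.1 limits the key table to the PI and the coordinator.

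The documents describe no separation or staged release of USE data, no masked arm code for the analysis, and no named holder of the allocation list.

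**The concern.** Blinding of data handlers and analysts is promised, yet the table they work in contains a near-marker of the arm. This is more than missing detail: following sections 5.1 and 9.1 as written produces that table.

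What is at stake in the analysis is freedom of choice. Section 7.4 selects the t-test or the Mann-Whitney test by the look of the distribution, and adds ANCOVA if confounding appears, without naming covariates. Choices of that kind are harmless when made blind. When the analyst can tell which group is VR, they can drift towards the favoured result without anyone intending it.

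What is at stake in the scoring is the rating itself. Participants are not blinded, and Appendix 3 marks each step as correctly completed or not, which is partly a matter of judgement. Blinded scoring is therefore an important protection for the mistakes component of the primary outcome.

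**Working it through.** The plan gives no figure for blinding, so there is none to reproduce. The check asks how well the arm can be read from the USE columns, and then who can see those columns.

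**Inputs**
- VR arm: USE requested by default (Summary, Novice Arm). Response share r is not given; r = 1 is assumed first.
- Control arm: USE only after opting into VR (same place). Opt-in share v is not given, so the whole range from 0 to 100% is shown.
- Allocation: 1:1 is assumed, in line with the equal groups in both sample-size statements (22 per group in the Summary, 16 per group in section 4.5). The result does not depend on which total applies.

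**Reading the arm from one row.** Call a row VR if USE is filled and control if it is empty. Every VR row is then right, and so is a share 1 − v of control rows:

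share correct = ½ × 1 + ½ × (1 − v) = (2 − v)/2

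Among rows with USE present, the share that are VR is 1/(1 + v).

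| Control opt-in v | Arms read correctly | VR among rows with USE |
|---|---|---|
| 0% | 100% | 100% |
| 20% | 90% | 83% |
| 50% | 75% | 67% |
| 75% | 62.5% | 57% |
| 100% | 50% (chance) | 50% |

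As a count, with 22 per group and v = 50%: 22 + 11 = 33 of 44, or 75%. With r = 1, an empty block is certainly a control.

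**If some VR participants do not respond.** The share correct becomes (r + 1 − v)/2. At r = 0.9 it is (0.9 + 1 − 0.2)/2 = 85% for v = 20%, and (0.9 + 1 − 0.5)/2 = 70% for v = 50%. The leak shrinks but disappears only if r = v.

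**Masked labels alone would not help.** Suppose the analyst received groups A and B. With r = 1, a single missing USE form shows which label is control, and so decodes the whole data set.

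**Who is exposed, role by role**
- *Data handlers and analyst.* They work in the table described in section 9.1, so the figures above apply to them. The analyst cannot simply do without USE data, because section 2 makes the comparison of novice and expert ratings an objective. The question is when the data are released.
- *Video scorer.* The study ID is an index, not an arm label. Without the allocation list or the combined table, a guess from the filename stays at 50%. No section gives the scorer either one, but none states who holds the list. Scoring takes place after the test, and USE forms also follow the test, so USE rows may already exist by then under the same ID.
- *PI and research coordinator.* Both can reach the key table and the videos. Their part in scoring or analysis is not stated, nor is whether the key table contains the allocation.
- *Prompter at the live test.* The USE form comes after the assessment, so it cannot influence the help given to that participant.

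**The case against.** The strongest reply is that none of this makes blinding impossible. The filename carries no arm information, the key table is restricted, and the scorer is named as having the videos and nothing else. The Summary already separates unblinded training staff from blinded assessment staff. A Data Management Plan appears on the attachment list in section 16; it was not available for this review and may contain access rules. The percentages also rest on an unknown opt-in rate, and they describe someone looking at the combined table, not the scorer or the prompter.

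Much of that stands. A reader might infer that the video filename unblinds the scorer, that the prompter is unblinded by the USE form, or that the trial cannot be called single blinded. The documents support none of these: the first needs a list or table that the scorer is not said to hold, the second has the timing the wrong way round, and the third depends on both. A reader might also want the resulting bias in the primary outcome. It cannot be derived, because section 4.5 gives a planning difference of 1 with neither unit nor standard deviation. Time to action, recorded in minutes and seconds in Appendix 3, is also less open to lenient rating than the yes/no marks.

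The reply does not reach the data handlers and the analyst. For them, sections 5.1 and 9.1 describe the exposure directly, and no safeguard is stated.

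**Conclusion.** The point holds for data handling and analysis: their blinding is promised but not protected by the procedures described. On the stated assumptions (1:1 arms, all VR participants returning USE), the arm can be read for between 50% and 100% of novices. It is 90% if a fifth of controls opt in and 75% if half do, and only universal opt-in brings it to chance. The same information would decode masked group labels. The consequence is that the data-dependent choices in section 7.4 may be made with knowledge of the arm.

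For video scoring the finding is weaker. Blinding is not assured, because the video ID also indexes the allocation and the USE rows, and custody of the list is left open. The documents do not show that it fails. For the live assessment no breach is shown.

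**What to change.** Amend the Blinding paragraph and sections 5.1 and 9.1 to state that:

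1. USE responses are kept in a separate file. They are not released to assessment data handlers, the scorer or the analyst until primary scoring is locked and the primary comparison has been run on masked arm codes.
2. Assessment videos carry a random code unrelated to the study ID.
3. The research coordinator holds the allocation list and the video code list, and takes no part in scoring or analysis.

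The cost is protocol wording, one additional file, one merge step and a second code list. No extra participants are needed. The face and content validity analysis is unaffected, because the USE data are released later, not withheld.

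Two further steps are optional good practice, since they answer no stated conflict: completing and locking the live record before the participant moves on to the USE form or the VR offer, and asking participants not to mention how they were trained.

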The accuracy with which the predefined sequence of steps is performed by the participant, defined as number of mistakes made and time taken, and amount of prompts/assistance required from the expert perfusionist.

Secondary outcomes

[figure not shown]
Additional data include participants views on the advantages and disadvantages of virtual reality training in the context of ECMO.

Additional study parameters

Data will be collected on the participants age, gender, experience with ECMO, and experience with VR usage.

Study type

This will be a hybrid study, with an expert & novice face & content study, and contained within the novice group, a single blinded randomised controlled trial.

Study population

Our study will recruit from two populations for the expert and novice arms of this study. For the former, 10 experts who are experienced perfusionists/intensivists with more than 6 years of experience with ECMO will be included. For the novice arm, the population will include intensive care nurses & cardiothoracic surgery nurses who work at one of the academic hospitals in the Netherlands, with no prior experience with ECMO.

Methods

The study is broadly divided into two arms: expert (experienced perfusionists / intensive care staff) and novices (Intensive care staff who have no experience with ECMO) and is summarised in Figure 1.

Novice Arm (Randomised Controlled Trial)

Novice participants will be allocated a study ID from 1-50 at the point of recruitment and randomised by an online research randomiser (<https://www.randomizer.org/>) between the instructional video (control) group and VR-ECMO sim (intervention) group. The control group will watch a video in which a perfusionist explains how to perform a circuit check for an ECMO patient on VA ECMO. The participants are then individually assessed using a real ECMO machine and ECMO doll, whereby they are asked to repeat the steps that they have been trained in. This assessment is recorded on video to be assessed later by an expert assessor, and an expert perfusionist & assessor will be present during the assessment

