In a related study on the VR-Extracorporeal Simulator (entitled “Virtual Reality Simulation as a Training Tool for Perfusionists in Extra Corporeal Circulation; Establishing Face and Content Validity” currently under peer-review), we showed that experts and novices alike found the simulator to be useful & realistic, and therefore valid for face and content validity. Due to the demonstration of feasibility in a closely related simulator, we aim to demonstrate face and content validity alongside concurrent validity in a single study for the VR-ECMO sim. We hypothesise that VR will enable participants to better learn and retain information through interactive engagement with a virtual reality ECMO simulator versus conventional training.

2. Objective(s)

In this study, the goal is to assess the face, content, and concurrent validity of the VR-ECMO sim by comparing the questionnaire ratings of novices and experts after completing the VR-ECMO sim, and comparing the novice intervention group who completed the VR-ECMO sim versus the control arm (video training) in terms of how well they are able to perform an ECMO circuit check, as rated by an expert.

3. Study type

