7.1 Main study parameters/endpoints

The accuracy with which the predetermined sequence of steps involved in an ECMO circuit check is performed by the participant. This is defined as number of mistakes made, and amount of prompts/assistance required from the expert perfusionist present at the assessment. Additionally, time to

accurately perform the predetermined endpoints/steps in the protocol of performing a circuit check as defined in Appendix 3.

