7.2 Secondary study parameters/endpoints

USE questionnaire (Appendix 2) to include participant ratings on the perceived usefulness, satisfaction, ease of use, and level of immersion of the VR-ECMO sim. Additional data include participants views on the advantages and disadvantages of virtual reality training in the context of ECMO.

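### The randomised comparison is labelled concurrent validity, but with no simulator performance score it can show only training effectiveness against an instructional video

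*Combined protocol and SAP*

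**What the plan says.** The aim appears in the Summary (Rationale) and again in section 1: "we aim to demonstrate face and content validity alongside concurrent validity in a single study for the VR-ECMO sim". Section 2 repeats the three validities as the goal and says how they will be assessed. Questionnaire ratings of novices and experts form one part. The other is "comparing the novice intervention group who completed the VR-ECMO sim versus the control arm (video training) in terms of how well they are able" to carry out a circuit check, as rated by an expert.

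On where performance is measured, the Summary (Methods, Novice Arm) says: "The participants are then individually assessed using a real ECMO machine and ECMO doll". Section 7.1 defines accuracy at that assessment as "number of mistakes made, and amount of prompts/assistance required from the expert perfusionist present at the assessment", and adds time. The scoring form is Appendix 3.

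On what is recorded about the simulator, section 7.2 lists the "USE questionnaire (Appendix 2) to include participant ratings on the perceived usefulness, satisfaction, ease of use, and level of immersion of the VR-ECMO sim", plus views on advantages and disadvantages. For experts, the Summary says: "Expert participants will not be randomised, and will all perform the VR-ECMO sim before completing the USE questionnaire". Their data are assigned to face and content validity.

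On data sources, section 5.1 opens with "Data will be extracted using online questionnaires" and then describes film of the physical assessments. Section 7.4 plans two-group tests, with ANCOVA where there is confounding.

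**The concern.** In its usual measurement sense, concurrent validity means that scores on an instrument agree with scores on a reference measure, taken in the same people at about the same time. If the instrument is the simulator, this needs a simulator score and a real-machine score from the same person. A difference between two randomised training groups on a real-machine test is a different quantity: the effect of one training method relative to another.

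The label matters because it governs what may be concluded. If the VR group does better, a report that follows the stated aim would present this as evidence of concurrent validity. A reader could then infer that performance in the simulator reflects real competence, for example that the simulator could be used to assess staff. If the VR group does no better than a good video, the same label could suggest that validity had been tested and had failed. Neither inference would follow from the data.

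**Working it through.** The point concerns design, and no figure in the plan needs to be reproduced. The check follows each group and each data stream, looking for a performance score obtained in the simulator.

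**By participant group** (Summary, Methods)

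- *Novices, VR arm:* train in the simulator, then take the physical assessment, then complete the USE questionnaire. Performance score: real machine only.
- *Novices, video arm:* watch the video, then take the physical assessment. They may afterwards try VR and complete the questionnaire. Performance score: real machine only.
- *Experts:* use the simulator and complete the questionnaire. No physical assessment is described for them. Performance score: none.

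**By data stream**

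- Section 7.1 (main endpoints): mistakes, prompts and time at the physical assessment.
- Section 7.2 (secondary): USE ratings and opinions. The Appendix 2 items are agreement ratings and free text, not performance.
- Section 7.3 (other): age, gender, ECMO experience and VR experience.
- Section 5.1: questionnaires and film of the physical assessments.
- Section 9.1: the database holds questionnaire data and assessment results, with the videos kept alongside.
- Appendix 3: 13 circuit-check steps, each marked as correct or not and timed, on the form for the physical assessment.

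No stream contains a simulator score.

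**Count.** With section 4.5's 32 novices and 10 experts, 32 + 10 = 42 participants. With the Summary's 44 novices, 44 + 10 = 54. Under either figure, the number with a simulator score paired with a real-machine score is 0. The difference between 32 and 44 does not affect this point.

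**By analysis.** Section 7.4 offers the t-test or Mann-Whitney test, the chi-squared or Fisher test, and ANCOVA. These compare groups. No correlation, agreement or calibration of simulator performance against real performance is planned. Section 4.5 likewise sizes the trial on a mean difference, not on a validity coefficient.

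**What the comparison estimates.** Randomised VR versus video, scored on the real machine after training, estimates the difference in post-training performance between those two methods. The relevant reference is the video. The Summary and section 1 describe usual training as apprenticeship and shadowing, and Appendix 2 also identifies conventional training with shadowing. Reading concurrent validity loosely, as comparison with the established method, therefore does not rescue the label, because the established method is not the comparator.

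**Missing figures.** Figure 1 and a figure under the Summary's secondary outcomes are not visible in the text reviewed. Section 7.2 gives the secondary endpoints in words, with no simulator performance measure, so the finding does not depend on the missing images.

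**The case against.** The strongest reply is that section 2 supplies its own working meaning. It says the validities will be assessed by the questionnaire comparison and by the VR-versus-video comparison. The endpoints in section 7.1, the Appendix 3 form and the tests in section 7.4 answer that second comparison. The documents nowhere define concurrent validity as agreement between paired scores; that definition comes from general usage.

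This part stands. A reader might infer from the missing simulator score that the third objective cannot be answered by any result. The documents do not support that: the objective as section 2 spells it out has data and an analysis. The fault is that the name does not fit the quantity.

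A second reply is that the training purpose is already clear. The Summary and section 1 hypothesise better learning and retention, and section 3.3 describes a comparison of a simulator with a video. That is true, and it helps a careful reader. It does not remove the validity claim, which stands as a headline aim in three places and would naturally be carried into the report.

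A third reply is that this is mere terminology, since nothing operational changes. The correction is indeed small, but the term claims a property that the design does not examine, so it changes what the trial may conclude.

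It may also be tempting to keep the term by correlating simulator logs with Appendix 3 results in the VR arm. The documents mention no such logs, and a score from the training session would be taken while the novice is still learning. That is not a sound basis for the claim.

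**Conclusion.** The concern holds as a mismatch between a stated aim and the design. The plan promises concurrent validity, but the randomised part can show only the training effectiveness of VR relative to an instructional video on a real-machine circuit check. It cannot show whether simulator performance tracks real performance, because the documented number of participants with a simulator performance score is 0 of 42 (or 0 of 54).

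The limit applies to the randomised comparison only. The USE ratings still serve the face and content validity aims, and the trial remains informative about training.

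Two assumptions carry the conclusion. The first is the usual measurement meaning of concurrent validity, which the documents neither state nor replace with another formal definition. The second is that sections 5.1, 7.1 to 7.3 and 9.1 list all the data to be collected.

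**What to change.** In the Summary rationale, section 1 and section 2, replace the term concurrent validity with: *training effectiveness of the VR-ECMO sim versus an instructional video, on the Appendix 3 assessment*. Leave the face and content validity aims as they are. State in section 2 or 7.4 that the conclusion from the randomised comparison is limited to this, and that it does not address whether performance in the simulator reflects performance on the machine.

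The cost is a rewording in three places, one added sentence and a narrower stated claim. Allocation, endpoints, sample size, analysis and participant procedures are unaffected. If the protocol has already been approved, the change can go through the amendment route in section 12.
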